- i. Investigator must check for acute illness or body temperature $\geq 38.0^{\circ}\text{C}/100.4^{\circ}\text{F}$ at the time of vaccination. If the vaccination visit cannot be rescheduled within the allowed window or the contraindications to vaccination persist, the sponsor's medical monitor should be contacted for further guidance.
- j. If a situation arises where a study blood draw and vaccination with a licensed vaccine occur on the same day, the blood draw should be made before the vaccination.
- k. After vaccination, participants will remain under observation at the study site for at least 30 minutes. Any solicited local (at injection site) and systemic AEs, unsolicited AEs, SAEs, concomitant medications, and vital signs will be documented by study-site personnel following this observation period and participants will be allowed to leave the study site at approximately 45 minutes post-vaccination.
- l. Following the 28th day after each vaccination, only concomitant medications associated to SAEs will be recorded.
- m. If an event is still ongoing on Day 8 or Day 64 the participant should keep the diary after the review and collect information until resolution. The diary should be reviewed again at the next visit.
- n. The screening colposcopy will be performed as study procedure only if a result of colposcopy performed within last 12 months is not available.

AE=adverse event; d=day; FU=follow-up; HIV=human immunodeficiency virus; HR-HPV=high-risk human papillomavirus; ICF=informed consent form; immuno=immunology; mo=month; PBMC=peripheral blood mononuclear cell; PCR=polymerase chain reaction; PI=principal investigator; SAE=serious adverse event; SRCN=screening; SRP=study responsible physician

ABBREVIATIONS

Ad26	adenovirus serotype 26
AE	adverse event
AIS	adenocarcinoma in situ
BN	Bavarian Nordic (A/S)
CI	confidence interval
CIN	cervical intraepithelial neoplasia
CSR	Clinical Study Report
DNA	deoxyribonucleic acid
eCRF	electronic case report form
eDC	electronic data capture
EDTA	ethylenediaminetetraacetic acid
ELISA	enzyme-linked immunosorbent assay
ELISpot	enzyme-linked immunospot
ER	emergency room
EU	European Union
FAS	Full Analysis Set
FDA	Food and Drug Administration
FIH	First-in-Human
GCP	Good Clinical Practice
GLP	Good Laboratory Practice
β-hCG	β-human chorionic gonadotropin
HIV	human immunodeficiency virus
HPV	human papillomavirus
HR	high-risk
HSIL	high-grade squamous intraepithelial lesion
ICF	informed consent form

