2. OBJECTIVES, ENDPOINTS, AND HYPOTHESIS

2.1. Objectives and Endpoints

Primary

Objectives	Endpoints
Primary To assess safety and reactogenicity of the 3 vaccine regimens.	
 • Solicited local and systemic adverse events (AEs) for 7 days after each vaccination. • Unsolicited AEs from the time of informed consent form (ICF) signature until 28 days after the first vaccination, and thereafter, until 28 days after the second vaccination. • Serious adverse events (SAEs) throughout the study.

Secondary

Objectives	Endpoints
To assess immunogenicity of the 3 vaccine regimens.	T cell responses to the separate or combined protein peptide pools of HPV16 and HPV18 E2, E6 and E7 proteins, including specific CD4 ⁺ and CD8 ⁺ T cells producing IFN γ , tumor necrosis factor alpha (TNF α), or interleukin 2 (IL-2) (combined cytokine expression may also be assessed) will be determined by flow cytometry.

Exploratory

Objectives	Endpoints

To assess the frequency and kinetics of clearance of
 
 • persistent or recently diagnosed HPV16 and HPV18 infection (combined^a) and • persistent or recently diagnosed HPV16 infection and • persistent or recently diagnosed HPV18 infection 
of the 3 vaccine regimens compared to placebo over the study period.
	
Healthcare provider- and self-collected cervical samples obtained over the study period will be genotyped by a qualitative HPV genotyping test (Cobas[®], Roche) and a quantitative HPV PRC genotyping test to evaluate HPV16 and/or HPV18 viral clearance^b, defined as:
 
 • A negative HPV16 genotype over the study period after having a baseline HPV16 infection (persistent or recently diagnosed); OR • A negative HPV18 genotype over the study period after having a baseline HPV18 infection (persistent or recently diagnosed).
To assess regression of CIN1 and concomitant clearance of HPV16 and/or HPV18 infection of the 3 vaccine regimens compared to placebo over the study period.	
 • Regression of CIN1: A colposcopic impression of normal after having a baseline of CIN1, AND concomitant clearance of baseline (persistent or recently diagnosed) HPV16 and/or HPV18 infection (as defined above).

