9. STUDY EVALUATIONS

9.1. Study Procedures

9.1.1. Overview

The **TIME AND EVENTS SCHEDULE** summarizes the frequency and timing of immunogenicity, safety and virology measurements applicable to this study.

Evaluation of the safety/reactogenicity of the vaccine regimens will include laboratory assessments, physical assessment by study-site personnel, and participant reports on signs and symptoms following vaccinations. Additional unscheduled study visits may be required if in the investigator's opinion, further clinical or laboratory evaluation is needed.

Participants will be provided with a thermometer (to measure body temperature), ruler (to measure local injection site reactions), and participant diary to record body temperature and solicited local (at injection site) and systemic events.

The diary includes instructions on how to capture the data and grading scales to assess severity of the symptoms. The study staff is responsible for providing appropriate training to the participant to avoid missing or incorrect data (refer to Study Training Manual). The diary card will be reviewed by the study personnel at visits indicated in the **Time and Events Schedule**.

If the diary card review is missed, the diary card will be reviewed in the following visit. If a participant misses a vaccination, the diary covering the period after the missed vaccination does not have to be filled in.

The total blood volume to be collected during the study from each participant will be approximately 485 mL, which is considered acceptable based on the US Department of Health and Human Services Office for Human Research Protections, and the US FDA guidelines.^{49,50}

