9.1.2. Visit Windows

Participants should be encouraged to come on the exact day planned and use the visit window only if necessary. For the following visits, windows will be allowed as indicated:

- Second vaccination: \pm 7 days

^a Depending on the time of the occurrence, any participant who receives a prohibited concomitant medication will not be included in the immunogenicity analyses.

- 7 days post-vaccination safety only visit: \pm 2 days
- 21 days post-Dose 2 vaccination safety, immunogenicity and virology visit: \pm 3 days
- 28 days post-vaccination safety only visit (telephone call): \pm 3 days
- 2 months post-Dose 2 vaccination safety and virology visit: \pm 5 days
- 6 months post-Dose 1 safety and virology visit: \pm 14 days
- 6 months post-Dose 2 vaccination safety, immunogenicity and virology visit: \pm 14 days
- 12 months post-Dose 1 safety, immunogenicity and virology visit: \pm 14 days

If a participant cannot be vaccinated within the allowed window, then that vaccination should not be administered. However, vaccination outside of the window (in particular if the window is missed due to a study pause) can be assessed on a case-by-case basis upon discussion between investigator and sponsor.

No visit windows are applicable for telephone calls to sentinel participants at 1 day post vaccination.

The timings of the second vaccination and of Visit 12 will be determined relative to the actual day of the first vaccination. The timing of visits 7, 8, 9, 10, 11 and 13 will be determined relative to the actual day of the second vaccination.

9.1.3. Screening Period (Days -42 to -2): Visit 1

Only participants complying with the inclusion and exclusion criteria specified in Section 4.1 and Section 4.2, respectively, will be included into the study. The investigator will provide detailed information on the study to the participants and will obtain written informed consent prior to each participant's participation in the study. All the procedures described in the [Time and Events Schedule](#) will only take place after written informed consent has been signed.

The following evaluations will be performed on participants to determine overall eligibility:

- Review of inclusion/exclusion criteria
- Demographic information
- Medical history and pre-study medications
- Physical examination including vital signs measurement (supine systolic and diastolic blood pressure, heart rate and oral temperature) and height and weight

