9.1.4.2. Post-first Vaccination Follow-Up

The randomization, vaccination process and safety evaluations described below for HPV16 infected participants will be performed in the same manner and independently among HPV18 infected participants.

- **1 Day Post-first Vaccination: Sentinel Participants: Visit 3**

At 1 day after the first vaccination, a telephone call will be made to the 5 sentinel participants (2 in Step 1 and 3 in Step 3); vaccination of additional participants will be halted until a 24-hour and 7-day post vaccination blinded safety review of solicited and unsolicited AEs are performed by the PI and the SRP.

- **7 Days Post-first Vaccination: Visit 4**

This visit will include an abbreviated physical examination (at the discretion of the investigator), vital signs measurement, and recording of any AEs/SAEs and concomitant medications. Samples for safety laboratory testing (hematology and biochemistry) will be collected. The participant diary will be collected and reviewed.

- **28 Days Post-first Vaccination: Visit 5**

This visit will be a telephone call to collect safety information (unsolicited AEs, SAEs and concomitant medications).

- **6 Months Post-first Vaccination (Week 26): Visit 12**

This visit will include an abbreviated physical examination (at the discretion of the investigator), vital signs measurement, self-collected cervico-vaginal sample for type-specific

HPV16 and HPV18 PCR and recording of any SAEs and concomitant medications (related to SAEs only).

- **12 Months Post-first Vaccination (Week 52): Visit 14**

This visit will include an abbreviated physical examination (at the discretion of the investigator), vital signs measurement, healthcare provider-collected cervical sample for type-specific HPV16 and HPV18 PCR, self-collected cervico-vaginal sample for type-specific HPV16 and HPV18 PCR and recording of any SAEs and concomitant medications (related to SAEs only). At this visit all participants will undergo a colposcopic evaluation and an HSV-2 serology test. Samples will be shipped and tested in a central sponsor designated laboratory. Samples for immunogenicity assessments will be collected.

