9.2. Study Evaluations

9.2.1. Safety

An IDMC will be commissioned to evaluate safety data over the course of the study and to review any events that meet a specific study pausing or stopping rule or any other safety issue that may arise. Details regarding the IDMC are provided in Section [11.8](#).

Any clinically relevant changes occurring from the signing of the ICF until 28 days after the first vaccination and from the second vaccination through the following 28 days must be recorded on the AE section of the eCRF. Outside these periods, reporting will be limited to all SAEs.

Any clinically significant abnormalities (including those persisting at the end of the study/early exit) will be followed by the investigator until resolution or until a clinically stable endpoint is reached. All AEs and laboratory data will be coded for severity according to the criteria presented in Section [12.1.3](#) (see [Attachment 2](#)).

The PI, together with the sponsor's SRP, will be responsible for the safety monitoring of the study, and will halt vaccination of further subjects in case any of the pre-specified pausing or stopping rules described in Section [11.9](#) have been met.

The study will include the following evaluations of safety and reactogenicity according to the time points provided in the [Time and Events Schedule](#):

Adverse Events

All AEs will be reported as specified in Section 12.

For solicited AEs, the following applies.

Solicited Adverse Events

After each vaccination, participants will remain under observation at the study site for at least 30 minutes for presence of any acute reactions and solicited events. In addition, participants will record solicited symptoms in a diary for 7 days post-vaccination. All participants will be provided with a diary and instructions on how to complete the Diary (Section 9.1.1). Diary information will be transcribed by the study personnel in the diary eCRF pages. Once a solicited symptom from a diary is considered to be of severity Grade 1 or above, it will be referred to as a solicited AE.

Solicited Injection Site (Local) Adverse Events

Participants will be asked to note in the diary occurrences of pain/tenderness, erythema and induration/swelling at the study vaccine injection site daily for 7 days post-vaccination (day of vaccination and the subsequent 7 days). The extent (largest diameter) of any erythema, and induration/swelling should be measured (using the ruler supplied) and recorded daily.

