- **Injection Site Pain/Tenderness**

Injection site pain (eg, stinging, burning) is an unpleasant sensory and emotional experience associated with actual or potential tissue damage and occurring at the immunization site (with or without involvement of surrounding tissue). Injection site tenderness is a painful sensation localized at the injection site upon palpation or movement of the limb. Due to subjective nature of the reaction, the severity assessment of pain/tenderness is self-reported (if a participant is unable to provide self-report, other reporters include parent/care giver or health care provider).²²

- **Injection Site Erythema**

Injection site erythema is a redness of the skin caused by dilatation and congestion of the capillaries localized at the injection site. It can best be described by looking and measuring.

- **Injection Site Swelling/Induration**

Injection site swelling is a visible enlargement of an injected limb. It may be either soft (typically) or firm (less typical). Injection site induration is a palpable thickening, firmness, or hardening of soft tissue, usually has well-demarcated palpable borders, can be visible (raised or sunken compared to surrounding skin), is often ‘woody’ to touch and has a flat shape. As differentiation between swelling and induration may be difficult without health care professional’s assessment, both symptoms have been combined to allow self-assessment by the participants. Both swelling and induration can best be described by looking and measuring.

Note: any other injection site events not meeting the above case definitions should be reported separately as unsolicited AEs.^{32,33}

Solicited Systemic Adverse Events

Participants will be instructed on how to record daily temperature using a thermometer provided for home use. Participants should record the oral body temperature in the diary in the evening of the day of vaccination, and then daily for the next 7 days approximately at the same time each day (preferably in the evening). If more than one measurement is made on any given day, the highest temperature of that day will be used in the eCRF. Temperatures to be taken 7 days after the vaccination at the end of the diary period, may be collected earlier to coincide with the clinic visit.

Fever is defined as endogenous elevation of body temperature $\geq 38^{\circ}\text{ C}$, as recorded in at least one measurement.³⁶

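### An early Visit 4 or Visit 8 lets the diary be collected up to two days before the solicited-event period ends

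*Protocol*

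**What the plan says.** Section 2.1 lists as the first primary endpoint "Solicited local and systemic adverse events (AEs) for 7 days after each vaccination". Section 9.2.1 defines the recording period for local events as "daily for 7 days post-vaccination (day of vaccination and the subsequent 7 days", in brackets in the original, and uses the same definition for systemic symptoms. Temperature is to be recorded "in the evening of the day of vaccination, and then daily for the next 7 days".

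Section 9.1.2 gives the "7 days post-vaccination safety only visit" a window of plus or minus 2 days. The Time and Events Schedule agrees: Visit 4 is on Day 8±2 and Visit 8 on Day 64±2. Sections 9.1.4.2 (Visit 4) and 9.1.4.3 (Visit 8) state that "The participant diary will be collected and reviewed" at these visits.

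Three provisions touch on the timing:
- Footnote m of the Time and Events Schedule: "If an event is still ongoing on Day 8 or Day 64 the participant should keep the diary after the review".
- Section 9.2.1, on the final temperature only: it "may be collected earlier to coincide with the clinic visit".
- Section 9.1.1: "If the diary card review is missed, the diary card will be reviewed in the following visit".

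**The concern.** The recording period and the collection rule do not fit together. A site can follow every instruction and still take the diary back before the endpoint period has closed. Entries that were never made cannot be recovered in the analysis, so this is a data-collection matter and not one that a statistical analysis plan could settle.

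Two uses of the data are exposed. Section 11.4 requires frequencies of solicited events by severity and by duration, and an event that starts in the missing days affects both. The 7-day reviews by the investigator and the sponsor's physician, and those by the IDMC, draw on solicited events and decide whether vaccination of further participants continues. In the sentinel steps each active regimen has one woman per HPV type, so one incomplete diary there is a noticeable share of the information.

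**Working it through.** The plan gives no figure of its own on this point. The sample-size bounds in Section 11.2 do not bear on it. The check is a calendar count.

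**Inputs**
- Diary period: day of vaccination plus 7 days (Section 9.2.1), so 1 + 7 = 8 daily entries, Days 1 to 8. After dose 2 on its target day they are Days 57 to 64.
- Visit window: Day 8±2 and Day 64±2 (Time and Events Schedule; Section 9.1.2), so Days 6 to 10 and 62 to 66.
- Collection: at the visit (Sections 9.1.4.2 and 9.1.4.3).

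**Formula.** Full diary days falling after collection = max(0, 8 − visit day) after dose 1, and max(0, 64 − visit day) after dose 2.

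| Visit day | Full days after collection | Share of 8 entries |
|---|---|---|
| 6 or 62 | 8 − 6 = 2 | 2/8 = 25% |
| 7 or 63 | 8 − 7 = 1 | 1/8 = 12.5% |
| 8 or 64 | 0 | 0% |
| 9–10 or 65–66 | 0 | 0% |

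**Does another provision close the gap?**
- Footnote m is tied to an event ongoing on Day 8 or 64. At a visit on Day 6 that status is not yet known, and an event that starts on Day 7 or 8 is not covered.
- The early-reading allowance applies to the last temperature. It does not extend to injection-site reactions or to the other systemic symptoms.
- The rule in Section 9.1.1 deals with a review that was missed, not with a diary collected too soon.
- Section 9.1.2 encourages attendance on the exact day but still permits an early visit.
- The calls at Visit 5 (Day 29±3) and Visit 10 (Day 85±3) list unsolicited events, serious events and concomitant medication. Section 12 defines unsolicited events as those not asked about in the diary, so a headache on Day 7 after early collection has no clear place to be recorded.

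None of these covers an early attender with no ongoing event.

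**The case against.** The best defence is that the practical loss is slight. Section 1.1 reports that with other Ad26-based vaccines solicited events usually began within 1 to 2 days and most resolved within 1 to 3. Participants are asked to use the window only when needed. Section 12.3.1 requires all adverse events to be recorded, so a late event may still be reported under another label. Section 11.9 requires related events of Grade 3 or above to be notified within 24 hours, independently of the diary. The diary instructions and training material, which are not part of the protocol, may tell participants to keep an unfinished card. All of this limits the size of the problem. It does not remove the conflict in the protocol text, and relabelled events would not be counted as solicited events.

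Four stronger readings are tempting, and the document does not support them:
- *A visit on Day 8 also loses that day's entry.* An evening time is set only for temperature, and for that reading an earlier measurement is allowed. Other symptoms are simply noted daily.
- *Affected women would appear as complete cases without events.* Entries are daily and are transcribed to the eCRF, so blank days can be seen. How they are handled is a matter for the analysis plan.
- *All 66 women are affected.* All are subject to the rule, but only those seen early can lose entries.
- *The safety reviews will run on Day 6 data.* They are specified as 7-day reviews and also cover unsolicited events, with laboratory results added for the IDMC. Nothing says that a shorter period counts. The risk is that the diary data for an early attender are incomplete when the review takes place.

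**Conclusion.** The point holds as a conflict between the diary period, the visit window and the collection rule. For a woman seen early with no ongoing event, up to 2 of 8 daily entries (25%) of a primary endpoint can go unrecorded after either dose. The loss is 1 of 8 (12.5%) for a visit one day early, and no full day is lost for a visit on or after Day 8 or 64.

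This assumes that sites collect the card at the visit as written and that no instruction outside the protocol overrides this. How many women would attend early is not known from the document. The number of events missed is probably small if onset follows the pattern seen with other Ad26-based vaccines. The correction is still worth making, because it concerns a primary endpoint in a first-in-human study and data that feed the 7-day reviews.

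**What to change.** In Sections 9.1.4.2 and 9.1.4.3 and in footnote m, state that at a Visit 4 or 8 held before Day 8 or Day 64 the diary is reviewed but stays with the participant until all 8 days are recorded. Obtain the remaining entries by a short contact on or just after Day 8 or 64. Collect the card at the next clinic visit, which is Visit 6 after dose 1 and Visit 9 after dose 2. The existing calls around Day 29 and Day 85 come too late to serve the 7-day reviews.

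Alternatively, remove the early half of the window for these two visits, leaving Days 8 to 10 and 64 to 66.

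In either case, reconcile the Time and Events Schedule and its footnote with Sections 9.1.2, 9.1.4.2, 9.1.4.3 and 9.2.1, so that the full diary period is available to each 7-day review. No participant's data should be left out of a review because her diary is incomplete: in a sentinel step that could remove the only woman on an active regimen.

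The cost is a sentence in each of two sections and in the footnote, one brief extra contact for early attenders and later return of some cards. The alternative costs a slightly narrower visit window.

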9.1.4.3. Post-second Vaccination Follow-Up

- **1 Day Post-second Vaccination (sentinel participants only): Visit 7**

This visit will be a telephone call to check participant diaries and to collect safety information (solicited and unsolicited AEs, SAEs and concomitant medications).

- **7 Days Post-second Vaccination: Visit 8**

This visit will include an abbreviated physical examination (at the discretion of the investigator), vital signs measurement, and recording of any AEs/SAEs and concomitant medications. Samples for safety laboratory testing (hematology and biochemistry) will be collected. The participant diary will be collected and reviewed.

- **21 Days Post-second Vaccination: Visit 9**

This visit will include an abbreviated physical examination (at the discretion of the investigator), vital signs measurement, self-collected cervico-vaginal sample for type-specific

HPV16 and HPV18 PCR and recording of any AEs/SAEs and concomitant medications. Samples for immunogenicity assessments will be collected.

- **28 Days Post-second Vaccination: Visit 10**

This visit will be a telephone call to collect safety information (unsolicited AEs, SAEs and concomitant medications).

- **2 Months Post-second Vaccination: Visit 11**

This visit will include an abbreviated physical examination (at the discretion of the investigator), vital signs measurement, a self-collected cervico-vaginal sample for type-specific HPV16 and HPV18 PCR and recording of any SAEs and concomitant medications (related to SAEs only).

- **6 Months Post-second Vaccination: Visit 13**

This visit will include an abbreviated physical examination (at the discretion of the investigator), vital signs measurement, self-collected cervico-vaginal sample for type-specific HPV16 and HPV18 PCR and recording of any SAEs and concomitant medications (related to SAEs only).

Samples for immunogenicity assessments will be collected.

